7.2.3. Urinalysis

A urine sample will be collected for urinalysis. The urinalyses will include urine pH, specific gravity, leukocyte, erythrocyte and protein.

The urinalysis will be performed at Screening, Day 84 ±7 days, Day 168±7 days (prior to dosing), Day 252 ±7 days and Day 336±7 days (or End of Study Visit).

The End of Study urinalysis for Protocol FP01C-13-001 will be used as the Baseline

assessment for this study.

Urine samples will be collected in the hospital or at the investigative site and will be sent to the Central Laboratory for analyses.

*If the patient completed 12 months of treatment with LMIS 50 mg more than 28 days prior to entering the Extension study, the testosterone level should be repeated and the repeat test should indicate that the patient maintains a castrate-level of testosterone. In addition, the ECOG, PE, ECG, laboratory and PSA tests should be repeated.

If the patient has completed 12 months of treatment with LMIS 50 mg under Protocol FP01C-13-001 within the last 28 days, they will be allowed to enter the Extension study without repeating the testosterone measurements, ECG, PE, laboratory and the PSA tests.

7.2.4. ECG

An ECG will be performed by standard 12-lead at the Screening Visit for eligibility and on Day 168±7 days prior to dosing and on Day 336±7 days (or End of Study Visit).

*If the patient completed 12 months of treatment with LMIS 50 mg more than 28 days prior to entering the Extension study, the testosterone level should be repeated and the repeat test should indicate that the patient maintains a castrate-level of testosterone. In addition, the ECOG, PE, ECG, laboratory and PSA tests should be repeated.

If the patient has completed 12 months of treatment with LMIS 50 mg under Protocol FP01C-13-001 within the last 28 days, they will be allowed to enter the Extension study without repeating the testosterone measurements, ECG, PE, laboratory and the PSA tests.

7.2.5 Adverse Events

Subjects will be asked to report adverse events voluntarily. The investigator will also question and examine the subjects to identify any adverse events at each visit (including Screening Visit). See **Section 9 Adverse Events (AE) and Serious Adverse Events (SAE)** for detailed information on adverse events.

8. Concomitant treatment

All concomitant medications, both permitted and prescribed, and significant non-drug therapies, such as surgery, blood transfusions and physical therapy, administered after the subject begins participation in this study will be recorded in the source documents and in the Concomitant Treatment Log in the CRF. Those records will include generic name / trade names (allowed for combination medication only), medical indication, total daily dose, route of administration and start and end dates of treatment.

The treatments recorded prior to and during participation in Protocol FP01C-13-001-EX will be recorded. Moreover, all concomitant medications administered for the treatment of an adverse event must be recorded.

8.1. Permitted treatment

- (1) Bisphosphonates will be permitted during the study.
- (2) Denosumab will be permitted during the study.
- (3) Supplementation of vitamin D and calcium will be allowed during the study if, in the investigator's opinion, it is needed for the patient's health.
- (4) Plain, over-the-counter multi-vitamins will be permitted during the study.
- (5) Glucocorticosteroids will be allowed if being used as a replacement therapy.
- (6) Pain medication will be allowed if it is an over-the-counter prescription medication and prescribed by a physician and as described in Appendix IV.
- (7) Oral hypoglycemics will be allowed for control of Type II diabetes.
- (8) Radiation for pain control will be allowed during the study.

Any use of concomitant treatment must be recorded on the CRF.

8.2. Prohibited treatment

The following medications are prohibited during the study period (from Screening Visit to EOS):

- (1) Other gonadotropin-releasing hormones
- (2) Other chemotherapy, immunotherapy, cryotherapy, radiotherapy for treatment of prostate carcinoma
- (3) Any OTC medication other than those listed in the Concomitant Treatment section.
- (4) Dietary supplements, herbal supplements, or herbal tea.
- (5) Insulin
- (6) Anti-androgens
- (7) 5-alpha reductase inhibitors
- (8) Systemic corticosteroids >10mg/d

Subjects who have received these prohibited treatments should be withdrawn from the trial.

8.3. Rescue medication and treatment

If the event of an emergency, the investigator will institute clinical life-support procedures according to the individual situation.

9. Safety Monitoring

9.1. Adverse events (AEs)

An adverse event (AE) is defined as any untoward medical occurrence in a subject or clinical investigation subject administered a pharmaceutical product which does not necessarily have a causal relationship with the treatment. An AE can therefore be any unfavorable and unintended sign, symptom, or disease temporally associated with the use of a medicinal product, whether or not considered related to the medicinal product. However, abnormal laboratory values or changes are not automatically reported as adverse events if they are not clinically significant. They will only be recorded as adverse events if a therapeutic action is needed or the investigator judges them to be clinically significant.

The occurrence of adverse events should be sought by non-directive questioning of the subject at each visit and/or telephone follow-up during the study. Adverse events also may be detected when they are volunteered by the subject during or between visits or through physical examination, vital sign measurement, laboratory test or other assessments. All adverse events must be recorded on the Adverse Events CRF with the following information:

1. AE term and description
2. Duration (onset and resolution dates or if continuing at final exam)
3. Severity grade (mild, moderate, severe, life-threatening, death)
4. Whether the AE constitutes a serious adverse event (SAE)
5. Relationship to the study drug (definite/possible/unrelated)
6. Action taken and treatment required
7. Outcome (recovered/resolved, recovered/resolved with sequelae, recovering/resolving, not recovered/not resolved, fetal)

9.1.1. The severity grade of AEs

The investigator will make an assessment of the maximum intensity that occurred over the duration of the event for all AEs reported during the study period using CTCAE version 4. The assessment will be based on the investigator's clinical judgment. The severity of each AE and SAE recorded in the CRF should be assigned to one of the categories described in [Table 9-1](#).

Table 9-1 Intensity scales of AE

Severity of AE	Description
Grade 1	Mild; asymptomatic or mild symptoms; clinical or diagnostic observations only; intervention not indicated.
Grade 2	Moderate; minimal, local or noninvasive intervention indicated; limiting age-appropriate instrumental activities of daily living (ADL)*.
Grade 3	Severe or medically significant but not immediately life-threatening; hospitalization or prolongation of hospitalization indicated; disabling; limiting self care ADL**.
Grade 4	Life-threatening consequences; urgent intervention indicated.
Grade 5	Death related to AE.

Activities of Daily Living (ADL):

*Instrumental ADL refer to preparing meals, shopping for groceries or clothes, using the telephone, managing money, etc.

**Self care ADL refer to bathing, dressing and undressing, feeding self, using the toilet, taking medications, and not bedridden.

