(10) Record any pre-treatment AE(s) NOTE: Open AEs from Protocol FP01C-13-001 will be recorded in this study file and noted in the database and other study documentation as, "AE under Protocol FP01C-13-001." These AEs should not be counted twice in the overall safety database.

*If the patient completed 12 months of treatment with LMIS 50 mg more than 28 days prior to entering the Extension study, the testosterone level should be repeated and the repeat test should indicate that the patient maintains a castrate-level of testosterone. In addition, the ECOG, PE, ECG, laboratory and PSA tests should be repeated.

If the patient has completed 12 months of treatment with LMIS 50 mg under Protocol FP01C-13-001 within the last 28 days, they will be allowed to enter the Extension study without repeating the testosterone measurements, ECG, PE, laboratory and the PSA tests.

6.2. Day 0 (approximately 6 months from last dose of LMIS 50 mg under Protocol FP01C-13-001)

Perform the following at 0 hr:

- (1) Record subject enrollment number prior to dosing (same enrollment number as was used in FP01C-13-001 will be used in this study)
- (2) Record vital signs prior to dosing
- (3) Record concomitant medication(s) prior to dosing
- (4) Record AE(s) prior to dosing and post dosing
- (5) Administer LMIS 50 mg.

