10. SAFETY ANALYSIS

10.1 Adverse Events

All AEs (whether treatment related or not) that occur before, during, or after dosing of the study medication will be recorded. The verbatim adverse event (AE) terms will be coded using the MedDRA dictionary, version18.1 or highest, and classified by System Organ

Statistical Analysis Plan

Class and Preferred Term.

Adverse events will be categorized as:

- Previous treatment-emergent adverse event (TEAE): The TEAEs are captured from previous FP01C-13-001 study.
- Newly treatment-emergent adverse event (TEAE): AEs occurring during or after the treatment period until the subject is off study, or before the first administration of study drug and worsen in severity for this FP01C-13-001-EX study.

Total treatment-emergent adverse event (TEAE): The combination of previous TEAEs and Newly TEAEs.

Unless otherwise specified, all adverse event summaries will include the previous TEAEs, Newly TEAEs and Total TEAEs. The listing of all TEAEs will be provided in Listing 16.2.7.1.

All AEs will be summarized by CTCAE version 4 grade and MedDRA preferred terms. The severity will be graded as follows:

- Grade 1 Mild; asymptomatic or mild symptoms; clinical or diagnostic observations only; intervention not indicated
- Grade 2 Moderate; minimal, local or noninvasive intervention indicated; limiting age-appropriate instrumental activities of daily living* (ADL)
- Grade 3 Severe or medically significant but not immediately life-threatening; hospitalization or prolongation of hospitalization indicated; disabling; limiting self-care ADL**
- Grade 4 Life-threatening consequences; urgent intervention indicated
- Grade 5 Death related to AE

Activities of Daily Living (ADL):

*Instrumental ADL refer to preparing meals, shopping for groceries or clothes, using the telephone, managing money, etc.

**Self-care ADL refer to bathing, dressing and undressing, feeding self, using the toilet, taking medications, and not bedridden.

The reasonable possibility of causation will be determined based on the investigator's clinical judgment as follows:

- **Definite:** A clinical event, including laboratory test abnormality, occurring in a plausible time relationship to drug administration, and which cannot be explained by concurrent disease or other drugs or chemicals.

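### The SAP's worsening rule for adverse events already open at Day 0 needs a Day 0 grade, but the protocol records only one maximum grade per event

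*Protocol*

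**What the plan says.** **Grading.** Protocol 9.1.1 has the investigator make an "assessment of the maximum intensity that occurred over the duration of the event for all AEs reported during the study period". The CRF items in Protocol 9.1 include one severity grade and the onset and resolution dates. They do not include a date of grade change.

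**Carry-over.** Under Protocol 6.1, item (10), "Open AEs from Protocol FP01C-13-001 will be recorded in this study file and noted in the database". These events carry a label marking them as parent-study events and must not be counted twice. The same item also collects new pre-treatment events.

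**Classification.** SAP 10.1 defines *Previous* events by source: "The TEAEs are captured from previous FP01C-13-001 study". *Newly* emergent events are those arising during or after treatment, or those "before the first administration of study drug and worsen in severity for this FP01C-13-001-EX study". *Total* combines the two. All adverse event summaries are to show the three columns unless otherwise specified, and the shells for Tables 14.3.1.1 to 14.3.1.10 do so. Listing 16.2.7.1 has one onset date, one Severity column and no *Previous*/*Newly* flag.

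**The concern.** To decide whether an event worsened in the extension, one needs its grade at Day 0 and its highest grade afterwards. The plan specifies neither. A single maximum over the whole event mixes the two periods, and for an event carried over from the parent study it includes year 1.

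Adverse event reporting is one of the primary endpoints, the study objective is safety over the added year, and the *Previous*/*Newly* columns are the only split by period in the adverse event tables. A misplaced event changes what the report says about the second year, most directly in the severity rows of Table 14.3.1.1 and in Tables 14.3.1.3, 14.3.1.5, 14.3.1.8 and 14.3.1.10.

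**Working it through.** The plan gives no figure to reproduce. The question is whether the class can be derived from the recorded fields.

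**Notation for a carried-over event.** Let m1 be the parent-study maximum grade (1 to 4), g0 the grade at Day 0, and m2 the maximum grade from Day 0 on (g0 to 5). I read worsening in SAP 10.1 as worsening after the first extension injection, that is m2 > g0.

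**Step 1. One overall maximum only.** The recorded grade is max(m1, m2). Grade 1 implies no worsening and grade 5 implies worsening. Grades 2, 3 and 4 each fit both answers. For example, a recorded grade 3 fits m1 = 3, g0 = 3, m2 = 3 (no change) and m1 = 3, g0 = 1, m2 = 3 (worsened).

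**Step 2. Parent maximum linked to the extension maximum.** Neither document specifies this step. The event is flagged when m2 > m1. Counting all patterns with g0 between 1 and m1:

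| m1 | Patterns | Worsened (m2 > g0) | Flagged (m2 > m1) | Missed (g0 < m2 ≤ m1) |
|---|---|---|---|---|
| 1 | 5 | 4 | 4 | 0 |
| 2 | 9 | 7 | 6 | 1 |
| 3 | 12 | 9 | 6 | 3 |
| 4 | 14 | 10 | 4 | 6 |
| All | 40 | 30 | 20 | 10 |

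Events that had not improved before Day 0 (g0 = m1) account for 4 + 3 + 2 + 1 = 10 of the 30, and all 10 are found. The 10 missed patterns are events that improved, stayed open, and rose again without passing the year-1 peak.

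**Step 3. Worsening before Day 0.** Protocol 4.1 (1) allows entry more than 28 days after the parent end-of-study visit. If an event worsens in that gap, g0 > m1. There are 3 + 2 + 1 = 6 patterns with m1 < g0 ≤ 4 and m2 = g0. None worsened after Day 0, yet all six are flagged as *Newly*. Step 2 shows no false flags only because it excludes this case.

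**Step 4. New events between screening and Day 0.** These have no parent-study grade, so there is nothing to compare with the single maximum.

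**Step 5. Column placement.** If a carried-over record is updated with a higher year-2 grade, it still meets the definition of *Previous*, so that grade appears in the year-1 column. If it is also classed as *Newly*, it meets both definitions, and the SAP does not say how its event count enters *Total* once.

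**Step 6. Scale.** SAP 4.3 caps enrolment at 137. One subject is 100/137 = 0.73 percentage points, and more if fewer enter.

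The counts in Steps 2 and 3 are of possible patterns, not expected frequencies.

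**The case against.** A reader might infer that the *Newly* class cannot be derived at all. The documents do not support that: if parent and extension records are graded separately and linked, any rise above the year-1 peak is recoverable. Recording one maximum grade per event is not a fault in itself; the problem is pairing it with a worsening rule.

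It is also tempting to say that every open event is affected and that the error always under-counts year 2. Carried-over events that stay stable or improve are correctly *Previous*, unless they had already worsened between the two studies. That exception, shown in Step 3, over-counts *Newly* events. Nor does an updated grade vanish, since it remains in *Total* and in Listing 16.2.7.1. A subject-level percentage in *Newly* changes only if the subject has no other qualifying event in that row.

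The strongest remaining defence is that the CRF is not among the documents. Protocol 6.2 has adverse events recorded before and after dosing at Day 0, so a pre-dose capture step exists. Protocol 9.3 asks for a serious event in a different time interval to be reported as a new event. These points carry some weight. However, neither provision asks for the current grade of an open event, the sentence before the one in 9.3 sends recurrence or progression of a serious event to the original episode as follow-up, and the listing shell shows no field for a Day 0 grade.

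**Conclusion.** The concern holds in limited form. For events open at Day 0 whose grade changes, the plan as written can put year-2 worsening in the wrong column or show it at the wrong grade:

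- a re-worsening up to the year-1 peak is missed;
- a year-2 peak in an updated carried-over record appears under *Previous*;
- worsening between the parent study and Day 0 can be counted as *Newly*;
- a new event recorded at screening has no reference grade.

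The size cannot be estimated, because the documents do not give the number of open events or how often they change grade. The conclusion rests on the protocol's field list and the SAP shells reflecting what is collected, and on worsening meaning a rise after the first extension injection. It is worth correcting because it affects the primary adverse event tables and the correction is cheap.

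**What to change.** **Protocol 6.1 (10) and 9.1.1.** For every event open at Day 0, record the grade before dosing and the maximum grade after the first extension injection. A linked record with its own date, opened when the grade rises, would serve in place of the second field.

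**SAP 10.1.** Define worsening as a post-Day-0 maximum grade above the Day 0 grade. Show the maximum grade before Day 0 under *Previous* and the maximum grade after Day 0 under *Newly*. Count a linked pair as one event, at its highest grade, in *Total*, so that the ban on double counting in Protocol 6.1 is kept.

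With both grades recorded, all 30 worsening patterns are classified correctly by construction, and so are the six gap patterns, because g0 replaces m1 as the reference. The cost is one extra CRF field (the Day 0 grade), a completion instruction, a few SAP sentences and slightly more programming. No visits or tests are added.

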9.1.2. The relationship to study drug

The investigator will make an assessment of the relationship between the study drug and the occurrence of each AE/SAE. The reasonable possibility of causation will be determined based on the investigator's clinical judgment. The causality should be considered as one of the categories described in [Table 9-2](#).

The adverse events should be followed until resolution or until the event is considered stable. Both regular return visits and telephone contacts may be required.

Table 9-2 The relationship between AE and study drug

Relationship	Description
Definite	A clinical event, including laboratory test abnormality, occurring in a plausible time relationship to drug administration, and which cannot be explained by concurrent disease or other drugs or chemicals.
Possible	A clinical event, including laboratory test abnormality, with a reasonable time sequence to administration of the drug, but which could also be explained by concurrent disease or other drugs or chemicals. Information on drug withdrawal may be lacking or unclear.

Unrelated A clinical event, including laboratory test abnormality, which is clearly not related to drug administration.

9.2. Serious adverse events (SAEs)

An SAE is any experience that suggests a significant hazard, contraindication, side effect or precaution. With respect to human clinical experience, this includes any event which:

- ◆ results in death,
- ◆ is life-threatening,
- ◆ requires inpatient hospitalization or prolongation of hospitalization, unless hospitalization is for:
 - routine treatment or monitoring of the studied indication, not associated with any deterioration in condition.
 - elective or pre-planned treatment for a pre-existing condition that is unrelated to the indication under study and has not worsened since the start of study drug
 - treatment on an emergency outpatient basis for an event not fulfilling any of the definitions of a SAE given above and not resulting in hospital admission
 - social reasons and respite care in the absence of any deterioration in the subject's general condition
- ◆ results in persistent of significant disability / incapacity, or
- ◆ is a congenital anomaly/birth defect,
- ◆ is a significant or important medical event that, based on appropriate medical judgment, may jeopardize the subject or may require intervention to prevent one of the other outcomes listed above.
- ◆ The medical monitor for this study is :

Contact number:

Email: [REDACTED]

9.3. Serious adverse events reporting requirement and emergency procedures

Whether or not related to the study medication, any adverse event which is fatal or life threatening that occurs during the study must be reported promptly (within 24 hours) to the sponsor (Foresee) or QPS. If reported to QPS, QPS will inform the sponsor on the same day or at the earliest possible time. At the time of the reporting, the following information should be provided if possible: study center, subject number, dose cohort during which the event occurred, a description of the event, date of onset and current status, outcome, action taken with the investigational drug, the reason why the event is classified as serious, and the investigator's current assessment of the association between the event and investigational drug.

Within the required timeframe, the investigator must provide further information on each SAE to Foresee/QPS, and QPS will assist the investigator in submitting the SAE to the appropriate IRB/EC, ADR reporting center and Foresee. The SAE/SUSAR (Suspected Unexpected Serious Adverse Reaction) will be reported to both competent authorities and relevant IRBs/ECs in accordance with the regulatory requirements of the country in which the SAE occurred.

Each recurrent episode, complication, or progression of the initial SAE should be reported as a follow-up to the original episode within 24 hours of the investigator's receiving the follow-up information. An SAE occurring at a different time interval or otherwise considered completely unrelated to a previous one should be reported separately as a new event.

9.4. Pregnancies

All subjects will be instructed to use adequate contraceptive precautions until the end of study. When pregnancy of a subject's spouse has been discovered, the pregnancy must be reported to sponsor/Contract Research Organization (CRO). The pregnancy outcomes, including spontaneous or voluntary termination, details of the pregnancy and birth, and the presence or absence of any birth defects, congenital abnormalities, or maternal and/or newborn complications, will be followed. The infant's medical record should be followed up to 1 year after birth.

10. Statistical Considerations and Analytical Plan

10.1. Sample Size

This a Safety Extension Study to Protocol FP01C-13-001. No efficacy analysis will be conducted under this protocol. No sample size calculations have been conducted for this study.

10.2. Analysis population

The Safety population will be used in the safety assessment for this study. The Safety population will consist of any subject receiving at least one dose of LMIS 50 mg under protocol FP01C-13-001-EX

